Appendix X:	Qualitative questionnaires for the Acceptability Assessment – Focus Groups with Malaria Surveillance Team
Appendix Y:	Swaziland Malaria Elimination Advisory Group (SMEAG) Terms of Reference
Appendix Z:	TPE Safety Monitoring Committee Terms of Reference

Study summary

Title	Evaluating the effectiveness and feasibility of reactive targeted parasite elimination (TPE) vs. reactive case detection (RACD) as a community-level intervention in response to a passively identified index case in Swaziland
Study design	Cluster randomized controlled trial
Aims	
Primary aim: To compare the impact of TPE versus RACD on malaria incidence.
 
Secondary aims
 
Effectiveness:
 
 1. To compare the impact of TPE versus RACD on seroprevalence. 2. To compare the impact of TPE versus RACD on prevalence of infection. 3. To compare the impact of TPE versus RACD on proportion of imported incident cases. 4. To compare the impact of TPE versus RACD on time to first post-intervention incident local case. 5. To compare the impact of TPE versus RACD on transmission potential as measured by relatedness of infections by microsatellite genotyping. 
Feasibility:
 
 1. To determine the feasibility of reaching 80% coverage for TPE versus RACD. 2. To evaluate the safety of TPE versus RACD. 3. To compare the acceptability of TPE versus RACD. 4. To compare the costs and cost-effectiveness of TPE versus RACD. 5. To measure the adherence to modified DOT with DP in the TPE arm.
Study site	Eastern endemic region of Swaziland, a very low endemic malaria elimination setting. A total of 287 health facilities and their catchment areas are located in this area.
Time frame	September 2015 until two transmission seasons completed (mid-2017)
Cluster or unit of randomization	At risk localities will be randomized to either TPE or RACD using a block stratified randomization based on risk rank (1-3) and population
Target area	For TPE localities: Neighborhood of individuals residing within 200m of an index case detected in passive surveillance. Individuals residing immediately beyond 200m will be included if a minimum of 30 individuals are not enrolled within 200m. For RACD localities: Neighborhood of individuals residing within 500m of an index case detected in passive surveillance.

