14.2 Outcome measures

Table 6. Outcome measures

Outcome	Indicator
Primary Aim	
Incidence	Cumulative incidence of all cases (Pf infection) identified by passive surveillance in the locality subsequent to the first reported case during the study period (not including additional cases found through RACD). Cases include both locally acquired and imported infections.
Secondary aims (effectiveness)	
Exposure (seroprevalence)	Seroprevalence to markers of recent exposure using ELISA in end-line survey samples taken from residents in Target Areas near the end of the study (expected mid 2017), excluding index cases detected through passive surveillance.
Infection prevalence	Prevalence of infection by LAMP and QTNASBA testing for gametocytes in LAMP positives in end-line survey samples taken from residents in Target Areas near the end of the study (expected mid 2017), including index cases detected through passive surveillance.
Time to first local post-intervention incident case	Time to first incident local case in the Target Area subsequent to the intervention. Target Areas that receive a repeat intervention will qualify to be included again at subsequent interventions.
Proportion of imported incident cases	Proportion of imported incident cases in the locality subsequent to the first reported case will be measured through passive surveillance. Additional cases found through RACD will not be included.
Transmission potential (by genotyping)	Microsatellite genotyping will be performed on samples collected from index cases as well as secondary cases.
Secondary aims (feasibility)	
Coverage	Proportion of persons residing within approximately 200m (TPE localities) or 500m (RACD localities) of the index case who consented to participate in the study and who completed the initial procedures for their study arm (finger prick for RDT in the RACD arm, initial dose of DP in the TPE arm)
Adherence	Proportion of persons who completed 3 days of therapy among all individuals initiated on DP in the TPE arm, as assessed by pill count
Prevalence of SAEs related to treatment	Proportion of subjects experiencing SAEs deemed possibly, probably, or definitely related to DP or AL, out of the total number of subjects enrolled
Acceptability	Qualitative assessment (See Section 10)
Cost	Cost per index case-level intervention, cost per case averted.

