Our primary study outcome is cumulative incidence of passively detected malaria infections in the overall population of the randomized study area localities. If incidence in the RACD arm remains as it was during the 2012-2015 transmission seasons (during which RACD was the standard of care) then given the above assumptions, we would expect cumulative incidence in the RACD arm to be 0.4% or approximately 4 per 1000 persons. If this is the case, our study would have 80% power to detect a reduction in cumulative incidence to 0.2% or 2 per 1000 persons if at least 51 of the 77 study localities had at least one index case (Table 7). Should cumulative incidence in the RACD arm rise to 0.5%, the reduction to 0.25 or 2.5 per 1000 persons in the TPE arm would be detectable with at least 47 localities with at least one case. Should cumulative incidence in the RACD arm fall to 0.3%, reduction to 0.15% or 1.5 per 1000 persons in the TPE arm would be detectable with 57 localities with at least one case. Because of the clustered nature of the data and the variability in cluster size, we used the harmonic mean of the population size (656 per locality, or 41328 total population using the harmonic mean of locality population).

Secondary outcome of effectiveness – Seroprevalence:

In the end-line survey near the end of the study (expected mid 2017), non-index cases residing in Target Areas will undergo blood testing to measure seroprevalence. Index cases will also be included as long as they were not the first index case for a Target Area. The first index case will not be included as this person's malaria exposure was known to occur pre-intervention. The sample size for the seroprevalence measure is expected to be 5400. Based on preliminary data, we expect seroprevalence to be approximately 3% prior to any intervention.[6]

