For the primary analysis comparing incidence between the TPE and RACD arms, we will follow an intention-to-treat (ITT) approach. We hypothesize that cumulative incidence in the TPE localities will be lower than in the RACD assigned localities. For the initial ITT analyses, estimates of effect will be unadjusted for any variables other than intervention group. To check for possible contamination of effects by proximity to an index case treated with TPE, a second set of ITT analyses will be conducted adjusting for intervention group and distance of index case from an index case assigned to TPE. Outcomes are assessed at the individual level. Because of the clustered nature of the data, our modeling approach will also adjust for correlation of observations by locality for analyses using the overall sample and by locality and index case for analyses using the Target Area sample. Generalized estimating equations (GEE) will be used to perform the proposed primary analyses. GEE accounts for the correlation of persons within clusters and localities. GEE estimates are consistent even if the correlation structure is miss-specified, though GEE's statistical efficiency improves as the working correlation structure more closely approximates the actual correlation structure. Thus, several working correlation structures suitable for the study's design will be considered (e.g., unstructured, Autoregressive order 1, exchangeable). The QIC statistic will be used to select the final working correlation structure. Robust Huber-White "sandwich" standard errors will be used to obtain correct inferences even if

the chosen correlation structure remains slightly miss-specified. Alpha will be set at 0.05 for all planned comparisons.

Should the preliminary analyses reveal an imbalance in the baseline covariates between the TPE and RACD arms, a second set of models will be run for all primary analyses. Adjusted models will reweight the data (through inverse probability weighting, or targeted minimum loss based estimation) to recover effect estimates that reflect an equal distribution of baseline covariates.

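### The primary GEE test does not reliably hold its 5% level: uncorrected sandwich errors push the error rate up, and leaving out the randomisation strata can pull it below 5%

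*Combined protocol and SAP*

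**What the plan says.** The Study summary gives the allocation of the 77 localities as "block stratified randomization based on risk rank (1-3) and population". Section 14.4 then sets out the primary comparison of incidence as an individual-level GEE clustered by locality:

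- **Terms.** "For the initial ITT analyses, estimates of effect will be unadjusted for any variables other than intervention group". Strata of risk return only as a descriptive subgroup.
- **Working correlation.** The candidates are meant to be ones suited to the study: "design will be considered (e.g., unstructured, Autoregressive order 1, exchangeable". Then: "The QIC statistic will be used to select the final working correlation structure".
- **Standard errors and level.** Huber-White errors are to give correct inference even if "the chosen correlation structure remains slightly miss-specified. Alpha will be set at 0.05 for all planned comparisons". No small-sample correction, reference distribution or sidedness is stated.
- **Other models.** One extra model adjusts for distance to a TPE index case. If baseline imbalance is found, "a second set of models will be run for all primary analyses", with reweighting by inverse probability or TMLE. Neither replaces the primary test.

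Section 14.1 expects 63 of the 77 localities to have a case. Table 6 in Section 14.2 counts cases "identified by passive surveillance in the locality subsequent to the first reported case during the study period", while Section 14.3 describes "cumulative incidence of passively detected malaria infections in the overall population of the randomized study area localities".

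**The concern.** Section 14.4 relies on the sandwich estimator to protect against a wrong working correlation. That protection is a large-sample property in the number of localities. With about 63 of them, rare events and sizes from 224 to 3,043, an uncorrected sandwich variance referred to a normal distribution tends to be too small, so the test rejects too often.

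Stratified allocation makes the arms more alike than simple allocation would. An arm-only variance does not credit this, so it is too large to the extent that rank predicts incidence, and the test then rejects too rarely. How well rank will predict incidence during the trial is unknown, so the true level of the one confirmatory test is unknown too.

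The QIC step adds a data-driven choice. Residents of a locality have no order, so AR(1) has no meaning for them, and an unstructured matrix cannot be estimated for localities of this size.

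**Working it through.** **The plan's own figures.** For the level of the test the plan gives only the nominal 0.05. Table 2, re-keyed, reproduces its totals: 63 localities with cases, 333 cases, 55,928 expected at risk, harmonic mean 656. Cases per 1,000 expected at risk, by rank:

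- rank 1: 208/27,061 = 7.7
- rank 2: 86/20,034 = 4.3
- rank 3: 39/8,833 = 4.4

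On total population the rates are 2.7, 1.1 and 0.7.

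**What the working correlation does.** With CV k = 0.9 and incidence p = 0.4% (Section 14.3), the intracluster correlation is k²p/(1-p) = 0.81 × 0.004/0.996 = 0.0033. The locality weights are:

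- exchangeable: n/[1+(n-1)ρ]
- AR(1): [n-(n-2)ρ]/(1+ρ)
- independence: n

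The largest-to-smallest weight ratio is 2.15 for exchangeable. It is 13.58 for AR(1), the same as for population (3,043/224 = 13.58). The effective number of localities, (Σw)²/Σw², is 61.6 with exchangeable weights and 44.6 with population weights. An AR(1) fit therefore behaves like independence.

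**Null simulation.** Both arms had 0.4%, with Table 2 sizes and ranks, gamma between-locality variation with total CV 0.9, and a two-sided z test at 1.96. Runs had up to 20,000 trials (Monte Carlo SE about 0.17 points at 20,000, 0.27 at 8,000). The actual strata and blocks were not available, so they are assumed: rank by population half (A-C), or blocks of 4 by population within rank (D). A-D are separately coded simulations. In two of them the GEE code was checked against standard software and agreed.

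Type I error (%), all cases counted, arm-only model, uncorrected errors:

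| Rank assumption | Exchangeable A / B / C / D | Population-type weights A / B / C / D |
|---|---|---|
| Uninformative | 6.6 / 6.9 / 6.3 / 6.6-6.7 | 7.7 / 7.8 / 7.4 / 7.4-7.7 |
| Rank 1 at twice ranks 2-3 | 5.5 / 5.3 / 5.3 / 5.6-6.2* | 6.5 / 6.8 / 6.2 / 6.6-7.0* |
| Table 2 at-risk rates | 6.0 / 6.2 / 5.4 / 5.6-6.2* | 7.4 / 7.3 / 7.0 / 6.6-7.0* |
| Strong (A-C: 2.7, 1.1, 0.7; D: 4:2:1) | 4.6 / 3.9 / 3.4 / 3.8-4.1 | 5.8 / 5.2 / 4.9 / 5.0-5.3 |

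*D's range covers mildly prognostic ranks in general, including the Table 2 pattern.

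**Which error does what.** Under simple allocation, exchangeable weights gave 7.3% on the Table 2 at-risk rates, against 5.7% under stratified allocation. On the total-population rates the pair was 6.6% against 3.5%. So the missing correction inflates, and the ignored strata deflate.

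**Repairing one error alone** (exchangeable):

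- Stratum terms with uncorrected errors: 7.0-8.6%.
- Mancl-DeRouen with t but no strata: about 2.6-5.4%, depending on rank.
- Stratum terms plus Mancl-DeRouen with t: 4.2-5.5%.
- Permutation within the strata: 4.5-5.3%.

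**Sensitivity** (exchangeable, A, the four rank assumptions in table order):

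- CV 0.6: 5.9 / 4.2 / 5.3 / 2.5%.
- CV 1.3: 7.5 / 6.7 / 7.3 / 6.2%.
- All 77 localities with total population: 6.5 / 5.2 / 5.7 / 3.5%.
- Cases after the first only, with about 48 localities contributing: 7.2 / 6.2 / 6.5 / 5.9%.
- Cases after the first only, all 63 kept (B): 6.4 / 5.8 / 5.7 / 3.6%.

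**The case against.** Several points against this have force.

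- **Cause.** A reader might infer that leaving the strata out inflates the error. It does not: it lowers it. Adding stratum terms while keeping uncorrected errors makes the test worse. The arm-only sentence is one of two opposing faults and not the source of the excess.
- **QIC.** Letting QIC choose between exchangeable and AR(1) gave up to 8.1% in simulation. A reader might take that as the plan's error rate. The documents do not support this, because the structures are listed only as examples and are limited to ones that suit the design. AR(1) does not suit it, and a careful analyst might never fit it.
- **A floor near 5%.** A reader might infer that the error falls only to about 4.6%, and only if rank is strongly prognostic. Three of the four simulations gave 3.4-4.1% for a strong rank, and with CV 0.6 a twofold rank effect already gives 4.2%.
- **Denominator.** On Section 14.3's wording (all 77 localities, total population) and the matching rank rates, the exchangeable test gave 3.5%, or 4.7% after the first case. On that reading it does not exceed alpha. The same reading with an uninformative rank gives 6.5% and 7.5%, so the dependence on rank remains.
- **Later detail.** The Section 18 timeline foresees an SOP for data analysis, which could hold a correction. Section 14.4 itself names none.
- **Permutation.** It holds 5% by construction within the strata simulated, so its result is no evidence that it beats a corrected, stratum-adjusted GEE.

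**Conclusion.** The concern holds in a limited form. As written, the primary test does not reliably have a 5% level. With a fixed exchangeable structure and all cases counted, the simulated error was 0.3 to 1.9 points too high when rank is uninformative or mildly prognostic, which includes the Table 2 at-risk pattern. It was 0.4 to 1.6 points too low when rank is strongly prognostic. Population-type weights add roughly another point. This is a modest defect, but it sits in the only confirmatory test, and its sign depends on something not known before the data are in.

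The figures assume the strata and blocks described, gamma heterogeneity, CV 0.9, two-sidedness and a z reference. Results for cases after the first depend on which localities are kept and should be read as indicative only.

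**What to change.** State in Section 14.4, before the data are analysed:

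1. One working correlation, exchangeable. Remove unstructured, AR(1) and QIC selection from the primary test.
2. One coherent primary inference that follows the randomisation and is valid with few clusters. Either form is acceptable:
   - the GEE with terms for the strata actually used (risk rank and population stratum), a Mancl-DeRouen-type variance and a t reference, giving both p-value and interval; or
   - a permutation test that re-draws the allocation within the actual strata and blocks, including localities added later as they were really assigned. If a GEE interval is reported beside it, state which decides. The permutation p-value and a corrected interval disagreed in 1-2% of null trials and 4-8% of trials at 0.4% against 0.2%.
3. Sidedness and the reference distribution.

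Do not make half the change: neither stratum terms with uncorrected errors nor corrected errors without strata.

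**Cost.** SAP wording only; no extra localities or data. Corrected intervals are about 6-7% wider. At 0.4% against 0.2%, power for the rank-adjusted corrected GEE against the planned exchangeable test fell from 69.1% to 64.2% (uninformative rank) and from 70.1% to 67.5% (Table 2 pattern). The permutation test changed power by -5.6 to +0.5 points with all cases counted, and by -7.0 to -3.9 with cases after the first. Part of each loss is the uncorrected test's excess error.

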4.3 Randomization of localities (clusters)

The randomization will be conducted by a member of the study personnel who is not directly involved in the field activities. A block stratified randomization method will be used to randomize the localities by risk

Table 2. List of study localities with case reports over the last 3 years with risk rank and total population (431 EA in 77 localities) and expected at-risk population (based on 105 EA with cases sept 2012-march 2015)

Data from Sept 2012-March 2015

Locality Code	Unique Locality Name	Risk Rank	Local Cases	Imported Cases	Incident Cases (Local + Imported)	Secondary Cases	Total Population	Historically at-risk population	Expected at-risk population
139000	MANZINIMAFUTSENI Mafutseni Bhudla	1	0	0	0	0	3498	1245	0
365000	LUBOMBOTIKHUBATI khuba Matsenjwa	2	0	0	0	0	2293	545	0
421000	LUBOMBOLUGONGOLWENI Mlawula Siweni	3	0	0	0	0	176	176	0
188000	HHOHHONTFONJENI Emsahweni Timpisini	2	0	0	0	0	719	719	0
428000	LUBOMBOMHLUMENI Ngomane Ngomane	2	0	0	0	0	2118	330	0
487000	LUBOMBODVOKODVWENI Macetjeni Mphosi	3	0	0	0	0	2419	529	0
482000	LUBOMBONKILONGO Big-Bend Mndobandoba	3	0	0	0	0	2470	558	0
129000	MANZINIMAFUTSENI Ngculwini Ntabamhlohana	1	0	0	0	0	1609	637	0
378000	SHISELWENIZOMBODZE Zombodze Mahlaba thini	3	0	0	0	0	1947	344	0
195000	HHOHHOMAYIWANE Herefords Jacks	3	0	0	0	0	1954	492	0
140000	MANZINIMAFUTSENI Mafutseni Ekuchwaleni	1	0	0	0	0	1824	287	0
471000	LUBOMBONKILONGO Sithobela Nkonjwa	3	0	0	0	0	50	50	0
180000	HHOHHOTIMPISINI Emvembili Mvembili	1	0	0	0	0	2534	436	0
419000	LUBOMBOMHLUME Simunye Lusoti	3	0	0	0	0	4014	576	0
426000	LUBOMBOMHLUMET shaneni Vuvulane	3	1	0	1	0	279	279	279
350000	LUBOMBOLUGONGOLWENI Siteki Mhlumeni	3	1	0	1	0	547	503	454
438000	LUBOMBOLOMAHASHA Lomahasha Ngulubeni	1	1	0	1	0	894	394	394
425000	LUBOMBOMHLUMET shaneni Tshaneni	3	0	1	1	0	2366	962	441
439000	LUBOMBOLOMAHASHA Lomahasha Matfuntini	1	1	0	1	0	1404	677	677
367000	LUBOMBOMPOLONJENI Maphungwane Magwanyana	1	1	0	1	0	1779	767	767
480000	LUBOMBONKILONGO Big-Bend Mayaluka	3	1	0	1	0	2305	353	353
366000	LUBOMBOTIKHUBA Mambane Mambane	2	1	0	1	0	4179	686	686
406000	LUBOMBOMPOLONJENI Mpholonjeni Lokhayiza	2	1	0	1	1	5561	592	592
412000	LUBOMBOMPOLONJENI Ngcina Nyetane	1	1	0	1	0	612	612	593
209000	HHOHHOMHLANGATANENI kambeni Mabiya	2	1	0	1	0	541	541	541
211000	HHOHHOMHLANGATANENI Sihhoye Mbangavene	2	1	0	1	1	3722	550	550
351000	LUBOMBOMPOLONJENI Maphungwane Sigwenyameni	2	0	1	1	0	2037	494	494

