14.3 Estimates of study power

Sample sizes and design effect estimates:

Sample size was driven by the number of localities within the area in the country considered to be at-risk for malaria transmission and the number of index cases we expect will be identified within those localities during the study period. The overall, Target Area, and adherence evaluation samples are described above in section 14.1. To estimate power to detect differences in cumulative incidence we used sample size of 55,928 for the overall sample. To estimate power to detect differences in seroprevalence, we used sample size of 5400 for the Target Area sample based on the assumptions as described above. As noted we used harmonic means for locality size (cluster size) in our estimates of power and design effect rather than arithmetic means to estimate more conservatively and to reduce the impact of the few localities with large population sizes.

We conducted sample size calculations to determine our ability to detect a difference in the effectiveness of TPE compared to RACD on incidence. We used the equations suggested by Hayes and Moulton (Cluster Randomized Trials, CRC Press, 2009) to calculate sample size required to detect a difference between arms.

Calculations are made for differences in proportion and assuming a coefficient of variation of 0.9 based on census and surveillance data from September 2012 to March 2015 to estimate the number of localities with cases, index cases and cluster size as described above. The power calculations are sensitive to sample size, but—in our study—the cluster population size is fixed. Sample sizes for primary and secondary outcomes can be found in Table 9.

Primary outcome – Cumulative Incidence:

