14.4 Analytical plan

Preliminary Analyses and Missing Data:

One-way frequency tables for all categorical variables and distributions, ranges, and outliers for continuous variables will be generated to perform range checks, quantify the amount of missing data, and yield valuable descriptive findings that will characterize coverage and cluster and Target Area characteristics in the study population. These analyses will also be stratified by randomization group (i.e., TPE vs RACD) using cluster-based two-group comparison methods (e.g., Rao-Scott chi-square) to check the equality of group covariates at baseline. Although we expect the randomization to produce balanced covariate structures, we will consider methods of adjustment to balance baseline covariates should there be significant differences between the TPE and RACD groups. To look for areas where there is a possibility of contamination by proximity of index cases assigned to different arms, we will describe the distances between TPE and RACD assigned index cases as well as the number of RACD assigned index cases who were within 2km of an index case assigned to TPE.

Primary Analysis:

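### The primary model omits the randomisation strata and each locality's 2012–15 incidence and adjusts for baseline only after a significance test; always adjusting could gain precision, by an amount the documents do not settle

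*Combined protocol and SAP*

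**What the plan says.** In section 14.4 (Primary Analysis) the primary comparison of cumulative incidence is a GEE in which, for the initial ITT analyses, "estimates of effect will be unadjusted for any variables other than intervention group". A second ITT analysis, always run, adds distance from an index case assigned to TPE as a check on contamination.

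Baseline covariates are handled separately. Under Preliminary Analyses the arms are compared with cluster-based tests, and "we will consider methods of adjustment to balance baseline covariates should there be significant differences between the TPE and RACD groups". Under Primary Analysis an imbalance leads to a further set of models that reweight the data by inverse probability weighting or targeted minimum loss estimation. The covariates are not listed, and baseline incidence is not named among them.

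The Study summary gives the randomisation as blocked and stratified on risk rank (1–3) and population. Neither appears as a term in the primary model. Table 2 in section 4.3 is headed "List of study localities with case reports over the last 3 years with risk rank and total population" and gives case counts and populations for all 77 localities. Section 14.3 draws on surveillance from the same period for its design inputs, "assuming a coefficient of variation of 0.9 based on census and surveillance data from September 2012 to March 2015".

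**The concern.** Incidence is very unequal between localities. Nine of the 77 hold 175 of the 333 incident cases in Table 2, so where a few hot localities fall by chance can move the estimate noticeably. A baseline rate known before randomisation is the natural covariate for absorbing part of that noise, and it has already been collected and used to set the design inputs.

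A significance trigger is a poor way to use it. Under randomisation any difference is due to chance, so a 5% test rarely fires, and in most trials the prognostic information is discarded. The decision is also taken after the data are open, on an unlisted set of covariates, with two differently worded triggers (a significant difference in one place, an imbalance in the other). What is at stake is precision in a trial that has little to spare, together with one avoidable analyst choice.

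**Working it through.** **Inputs.** RACD 0.4% and TPE 0.2% (section 14.3 and Table 7); n = 656 persons per locality (harmonic mean) and k = 0.9 (section 14.3); 63 localities expected to contribute, 31.5 per arm (section 14.1); alpha 0.05 (section 14.4). Sidedness is not stated, but Table 7 reproduces with z = 1.96. Re-keying Table 2 reproduces its totals (333 cases; 211,189, 71,661 and 55,928 persons) and the harmonic mean (656.3).

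**Step 1: the plan's own figure.** The unmatched cluster formula is

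c per arm = 1 + (1.96 + 0.84)² × {[p0(1−p0) + p1(1−p1)]/n + k²(p0² + p1²)} / (p0 − p1)²

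- Within-locality term: (0.003984 + 0.001996)/656 = 9.12 × 10⁻⁶
- Between-locality term: 0.81 × (0.000016 + 0.000004) = 16.20 × 10⁻⁶
- Sum 25.32 × 10⁻⁶, divided by 4 × 10⁻⁶ = 6.33
- c = 1 + 7.84 × 6.33 = 50.6

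This matches the 50.6 in Table 7, but the formula yields localities per arm, whereas the table labels it the total and halves it. That is a separate issue. Here it fixes the starting point: with 31.5 per arm, power = Φ(√(30.5/6.33) − 1.96) = Φ(0.235) = 59%.

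**Step 2: how much a covariate could remove.** The between-locality share of the variance is 16.20/25.32 = 64%. Only this part can be reduced.

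**Step 3: effect of adjusting.** Baseline counts are noisy. At 333/55,928 = 0.595%, a locality of 656 expects 3.9 cases, so the reliability is R = 0.81/(0.81 + 1/3.9) = 0.76. Replace k² by k²(1 − rho² × R). At rho 0.5, for example, 0.81 × (1 − 0.25 × 0.76) = 0.656; the between-locality term becomes 13.12 × 10⁻⁶, the sum 22.24 × 10⁻⁶, and the ratio 22.24/25.32 = 0.88.

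| rho (assumed) | Variance vs unadjusted | Power, 63 localities | Localities per arm for 80% |
|---|---|---|---|
| 0 | 1.00 | 59% | 50.6 |
| 0.3 | 0.96 | 61% | 48.4 |
| 0.5 | 0.88 | 65% | 44.6 |
| 0.7 | 0.76 | 71% | 38.8 |
| 0.9 | 0.61 | 80% (80.5%) | 31.1 |

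These figures precede the degree-of-freedom cost. One df of about 61 adds about 1.7% to the variance. Break-even is where 0.64 × 0.76 × rho² is about 0.017, that is, rho about 0.18. Stratum terms would cost a little more; their number is not known from the text available, and neither their cost nor their benefit is in the table.

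**Step 4: simulation check.** 2,000 trials per setting used the 63 case localities' expected at-risk populations, a locality-level log-linear Poisson model with small-sample robust standard errors, simple randomisation, and a raw +0.5 offset in the covariate. The third column adjusts for baseline incidence only when a 5% test of it is significant, as a stand-in for the plan's trigger.

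| rho | Variance ratio, always adjust | Variance ratio, test then adjust | Power, unadjusted → always adjusted |
|---|---|---|---|
| 0 | 1.02 | 1.00 | 65% → 64% |
| 0.3 | 0.97 | 1.00 | 63% → 62% |
| 0.5 | 0.90 | 0.98 | 63% → 66% |
| 0.7 | 0.78 | 0.96 | 64% → 73% |
| 0.9 | 0.56 | 0.93 | 64% → 83% |

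The test fired in about 5% of trials. With no treatment effect, rejection was 5–7% for both the unadjusted and the always-adjusted test.

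**Step 5: do the strata already do the job?** In Table 2, risk rank explains about 2–7% of the variance in log incidence, depending on specification, and about 9% on the raw rate scale. With population added, it explains about 8–12% of the variance in log incidence. Against past counts, then, the strata carry little of the same information.

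**Step 6: form of the covariate.** Expected at-risk population is 0 in the 14 localities without cases, so a rate on that column is undefined there. Historically at-risk population is non-zero in all 77. A raw offset on it is unstable: locality 471000 (0 cases, 50 people) gets 0.5/50 = 1.0%, sixth highest of 77 and above the locality with 22 cases (22.5/2,377 = 0.95%). In all, 37 of 77 localities have 0 or 1 case. A gamma–Poisson shrunken rate avoids this. With mean 333/71,661 = 0.465% and shape 1/0.81 = 1.23, the prior weight is 1.23/0.00465, about 266 persons. The two localities become 1.23/(50 + 266) = 0.39% and 23.23/(2,377 + 266) = 0.88%.

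**The case against.** The strongest reply is that an unadjusted randomised comparison is valid and always reported, the triggered models only add to it, and the gain rests on an unknown rho. This largely stands. The documents give reasons for caution about persistence: imported cases count in the primary outcome, the imported share rose from 51% to 71% (section 1.1), and new hotspots are anticipated (section 4.1). Against that, the plan itself uses past locality cases to predict which localities will contribute (section 14.1) and describes hot spots as places of highest future risk (section 1.2). That supports a positive rho but does not give its value.

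It is also fair that the text of section 4.3 breaks off where Table 2 begins, so whether past incidence also informed the randomisation cannot be settled. The risk ranks are said to reflect historical and recent transmission. Step 5 compares rank with noisy past counts, not with trial-period incidence. The simulation is not the planned individual-level GEE and omits the 14 zero-case localities.

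Some stronger readings are tempting but not supported:

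- A reader might infer that the reweighted models cannot be fitted because questionnaire covariates exist only for Target Area residents. The covariates are unlisted and section 14.4 mentions cluster characteristics, so locality-level variables could be used.
- A reader might infer that nothing is adjusted without a test. The distance-adjusted analysis is unconditional; the trigger concerns baseline covariates only.

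**Conclusion.** The point holds as one of efficiency and pre-specification. The primary model omits the strata and a prognostic baseline measure already in hand, and the test-then-adjust route recovers little of what that measure offers. At the plan's inputs and 63 localities, always adjusting moves power from about 59% to between 61% (rho 0.3) and 80% (rho 0.9). Below rho of about 0.18 there is a small loss, under 2% of variance at rho 0 for a single covariate. The result assumes k = 0.9, two-sided 5%, the harmonic-mean locality size and baseline reliability 0.76; rho is an assumption throughout.

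A reader might infer that the precision is free, or that adjustment restores the planned power. Neither follows. Degrees of freedom are spent, the denominators are 2007 census figures, and 80% is reached only near rho 0.9. The gap between 59% and the plan's 80% comes from the labelling of Tables 7 and 8, which needs its own correction.

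**What to change.** In section 14.4:

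1. Define the primary ITT model as arm + randomisation strata (risk rank and population, as randomised) + locality baseline incidence for September 2012 to March 2015 from Table 2, whatever the observed balance.
2. Use the historically at-risk population as the denominator and a form that is stable for zero or few cases, such as the log of an empirical-Bayes shrunken rate, with its formula written out.
3. State a rule for localities added under section 4.1: for example, the same-period count from the same surveillance source, and what is done if none exists.
4. Report the arm-only model as a sensitivity analysis.
5. Delete the significance-test trigger, and limit any further adjustment to named locality-level variables fixed before randomisation.

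The cost is SAP wording and a few degrees of freedom, with a small loss of precision if past incidence does not predict trial incidence. No new data are needed for the 77 listed localities.
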